APPENDIX 3. LABORATORY ASSESSMENTS

Laboratory parameter		Grading Scale	a) Gradable with Toxicity Grading Scale for Healthy Adult and Adol Volunteers Enrolled in Preventive Vaccine Clinical Study b) Gradable with Common Terminology Criteria for Adverse Events Version 4.03 c) Gradable with University of Delaware Criteria (http://www1.udel.edu/mls/mclane/KMS3RR.html) d) Not Gradable			
			Grade 1	Grade 2	Markedly Abnor	
				Grade 3		
Blood chemistry						
ALT / ALAT		a	$\geq 1.1 \times \text{ULN} - < 2.5 \times \text{ULN}$	$\geq 2.5 \times \text{ULN} - < 5.0 \times \text{ULN}$	$\geq 5.0 \times \text{ULN} - < 10 \times \text{ULN}$	$\geq 10 \times \text{ULN}$
AST / ASAT		a	$\geq 1.1 \times \text{ULN} - < 2.5 \times \text{ULN}$	$\geq 2.5 \times \text{ULN} - < 5.0 \times \text{ULN}$	$\geq 5.0 \times \text{ULN} - < 10 \times \text{ULN}$	$\geq 10 \times \text{ULN}$
Gamma glutamyl transpeptidase (g-GT)		b	$\geq 1 \times \text{ULN} - < 2.5 \times \text{ULN}$	$\geq 2.5 \times \text{ULN} - < 5.0 \times \text{ULN}$	$\geq 5.0 \times \text{ULN} - < 20.0 \times \text{ULN}$	$\geq 20.0 \times \text{ULN}$
Total bilirubin	(Liver Function test normal*)	a	$\geq 1.1 \times \text{ULN} - < 1.25 \times \text{ULN}$	$\geq 1.25 \times \text{ULN} - < 1.5 \times \text{ULN}$	$\geq 1.5 \times \text{ULN} - < 1.75 \times \text{ULN}$	$\geq 1.75 \times \text{ULN}$
	(Liver Function test increase*)	a	$\geq 1.1 \times \text{ULN} - < 1.5 \times \text{ULN}$	$\geq 1.5 \times \text{ULN} - < 2.0 \times \text{ULN}$	$\geq 2.0 \times \text{ULN} - < 3.0 \times \text{ULN}$	$\geq 3.0 \times \text{ULN}$
AP (ALP)		a	$\geq 1.1 \times \text{ULN} - < 2.0 \times \text{ULN}$	$\geq 2.0 \times \text{ULN} - < 3.0 \times \text{ULN}$	$\geq 3.0 \times \text{ULN} - < 10 \times \text{ULN}$	$\geq 10 \times \text{ULN}$
BUN		a	$\geq 8.211 - < 9.75 \text{ mmol/L}$	$\geq 9.75 - < 11.625 \text{ mmol/L}$	$\geq 11.625 \text{ mmol/L}$	Require
Total protein		a	$> 55 - \leq 60 \text{ g/L}$	$> 50 - \leq 55 \text{ g/L}$	$\leq 50 \text{ g/L}$	NA
Albumin		a	$> 27 - \leq 31 \text{ g/L}$	$> 25 - \leq 27 \text{ g/L}$	$\leq 25 \text{ g/L}$	NA
Glucose	Hyperglycemia	a	$\geq 5.55 - < 6.105 \text{ mmol/L}$	$\geq 6.105 - < 6.9375 \text{ mmol/L}$	$\geq 6.9375 \text{ mmol/L}$	Insulin hyperos
	Hypoglycemia	a	$\geq 3.6075 - < 3.8295 \text{ mmol/L}$	$\geq 3.0525 - < 3.6075 \text{ mmol/L}$	$\geq 2.4975 - < 3.0525 \text{ mmol/L}$	$< 2.4975 \text{ mmol/L}$
eGFR (Any eGFR value > 90 will be classified as Grade 0)		b	$\leq 90 - > 60 \text{ ml/min/1.73 m}^2$	$\leq 60 - > 30 \text{ ml/min/1.73 m}^2$	$\leq 30 - > 15 \text{ ml/min/1.73 m}^2$	$\leq 15 \text{ ml/min/1.73 m}^2$
LDH		d	NA	NA	NA	NA

Document: K:\AAA\Ga-PSMA-R2\VYA27826\Biostatistics\Documentation\SAP\v2.0\Ga-PSMA-R2-SAP
 Author: [Redacted]

Template No.: CS_TP_BS016 Revision 5
 Effective Date: 01Apr2018

Statistical Analysis Plan

Laboratory parameter		Grading Scale	a) Gradable with Toxicity Grading Scale for Healthy Adult and Adolescent Volunteers Enrolled in Preventive Vaccine Clinical Study b) Gradable with Common Terminology Criteria for Adverse Events Version 4.03 c) Gradable with University of Delaware Criteria (http://www1.udel.edu/mls/mclane/KMS3RR.html) d) Not Gradable				
			Grade 1	Grade 2	Grade 3	Markedly Abnormal	
Corrected Calcium	Hypercalcemia	a	>=2.625 - <2.75 mmol/L	>=2.75 - <2.875 mmol/L	>=2.875 - <3 mmol/L	>= 3 mmol/L	
	Hypocalcemia	a	>=2 - <2.1 mmol/L	>=1.875 - <2 mmol/L	>=1.75 - <1.875 mmol/L	<1.75 mmol/L	
Serum creatinine		a	>=132.6 - < 150.28 umol/L	>=150.28 - <176.8 umol/L	>=176.8 - <221 umol/L	>= 221 umol/L requires recheck	
Sodium	Hypernatremia	a	>=144 - <145 mmol/L	>=145 - <147 mmol/L	>=147 - <150 mmol/L	>=150 mmol/L	
	Hyponatremia	a	>=132 - <134 mmol/L	>=130 - <132 mmol/L	>=125 - <130 mmol/L	<125 mmol/L	
Potassium	Hyperkalemia	a	>=5.1 - <5.2 mmol/L	>=5.2 - <5.4 mmol/L	>=5.4 - <5.6 mmol/L	>= 5.6 mmol/L	
	Hypokalemia	a	>=3.5 - <3.6 mmol/L	>=3.3 - <3.5 mmol/L	>=3.1 - <3.3 mmol/L	< 3.1 mmol/L	
Uric acid		b	>ULN - 10 mg/dL (0.59 mmol/L) without physiologic consequences	NA	>ULN - 10 mg/dL (0.59 mmol/L) with physiologic consequences	>10 mg mmol/L	
Chloride		d	NA	NA	NA	NA	
Hematology							
RBC		d	NA	NA	NA	NA	
White blood cells with differential	WBC	Increased	a	>=10.8 - <15 10 ⁹ /L	>=15 - <20 10 ⁹ /L	>=20 - <25 10 ⁹ /L	>= 25 10 ⁹ /L
		Decreased	a	>2.5 - <=3.5 10 ⁹ /L	>1.5 - <=2.5 10 ⁹ /L	>1 - <=1.5 10 ⁹ /L	<= 1 10 ⁹ /L
	Monocytes		d	NA	NA	NA	NA
	Eosinophils		a	>=0.65 - <1.5 10 ⁹ /L	>=1.5 - <5 10 ⁹ /L	>=5 10 ⁹ /L	Hyperleukocytosis

Document: K:\AAA\Ga-PSMA-R2\VYA27826\Biostatistics\Documentation\SAP\v2.0\Ga-PSMA-R2-SAP_...
 Author: [Redacted]

Template No.: CS_TP_BS016 Revision 5
 Effective Date: 01Apr2018

Statistical Analysis Plan

Laboratory parameter	Grading Scale	a) Gradable with Toxicity Grading Scale for Healthy Adult and Adol Volunteers Enrolled in Preventive Vaccine Clinical Study b) Gradable with Common Terminology Criteria for Adverse Events Version 4.03 c) Gradable with University of Delaware Criteria (http://www1.udel.edu/mls/mclane/KMS3RR.html) d) Not Gradable				
					Markedly Abnor	
		Grade 1	Grade 2	Grade 3		
Basophils	d	NA	NA	NA	NA	
Lymphocytes	a	>0.75 – <=1 10 ⁹ /L	>0.5 – <=0.75 10 ⁹ /L	>0.25 – <=0.5 10 ⁹ /L	<= 0.25	
Neutrophils	a	>1.5 – <=2 10 ⁹ /L	>1 – <=1.5 10 ⁹ /L	>0.5 – <=1 10 ⁹ /L	<= 0.5	
Platelets	a	>125 – <=140 10 ⁹ /L	>100 – <=125 10 ⁹ /L	>25 – <=100 10 ⁹ /L	<= 25 1	
Hb	(Male) - gm/dL	a	>12.5 – <=13.5	>10.5 – <=12.5	>8.5 – <=10.5	<= 8.5
	(Male) change from baseline value – gm/dL	a	Any decrease – >1.5	>=1.5 – >2.0	>=2.0 – <5.0	>= 5.0
MCV	d	NA	NA	NA	NA	
Hematocrit	d	NA	NA	NA	NA	
PSA	d	NA	NA	NA	NA	
Urinalysis						
Appearance	d	NA	NA	NA		
Color	b	Discoloration	NA	NA		
pH	d	NA	NA	NA		
Specific gravity	d	NA	NA	NA		
Glucose	a	Trace	1+	2+	Hospita hypergl	
Occult blood	d	NA	NA	NA		
RBC/hpf	a	>=1 - <10	>=10 – <50	>= 50 and/or gross blood	Hospita packed (PRBC)	
WBC/hpf	c	NA	NA	NA	NA	
Casts/lpf	c	NA	NA	NA	NA	

Document: K:\AAA\Ga-PSMA-R2\VYA27826\Biostatistics\Documentation\SAP\v2.0\Ga-PSMA-R2-SAP
 Author: [Redacted]

Template No.: CS_TP_BS016 Revision 5
 Effective Date: 01Apr2018

Statistical Analysis Plan

Laboratory parameter	Grading Scale	a) Gradable with Toxicity Grading Scale for Healthy Adult and Adol Volunteers Enrolled in Preventive Vaccine Clinical Study b) Gradable with Common Terminology Criteria for Adverse Events Version 4.03 c) Gradable with University of Delaware Criteria (http://www1.udel.edu/mls/mclane/KMS3RR.html) d) Not Gradable			
		Grade 1	Grade 2	Grade 3	Markedly Abnor
Protein (dipstick test accepted)	a	Trace	1+	2+	Hospita dialysis

* This is not specified in FDA guidance. Therefore, we take as reference to the Hy's Law criteria for potential Function parameters to be taken in to account are Aspartate transaminase (AST) and Alanine transaminase (A

[figure not shown]
Document: K:\AAA\Ga-PSMA-R2\VYA27826\Biostatistics\Documentation\SAP\v2.0\Ga-PSMA-R2-SAP_ \

Author: [Redacted] \

Template No.: CS_TP_BS016 Revision 5 F

Effective Date: 01Apr2018

 Statistical Analysis Plan

[figure not shown]

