Illness or clinical adverse event (as defined according to applicable regulations)	No interference with activity	Some interference with activity not requiring medical intervention	Prevents daily activity and requires medical intervention	ER visit or hospitalization

B. Tables for Laboratory Abnormalities

The laboratory values provided in the tables below serve as guidelines and are dependent upon institutional normal parameters. Institutional normal reference ranges should be provided to demonstrate that they are appropriate.

Serum *	Mild (Grade 1)	Moderate (Grade 2)	Severe (Grade 3)	Potentially Life Threatening (Grade 4)**
Sodium – Hyponatremia mEq/L	132 - 134	130 - 131	125 - 129	<125
Sodium – Hypernatremia mEq/L	144 - 145	146 - 147	148-150	>150
Potassium – Hyperkalemia mEq/L	5.1 - 5.2	5.3 - 5.4	5.5 - 5.6	> 5.6
Potassium – Hypokalemia mEq/L	3.5 - 3.6	3.3 - 3.4	3.1 - 3.2	< 3.1
Glucose – Hypoglycemia mg/dL	65 - 69	55-64	45 - 54	< 45
Glucose – Hyperglycemia Fasting – mg/dL Random – mg/dL	100 – 110 110 – 125	111 – 125 126 – 200	>125 >200	Insulin requirements or hyperosmolar coma
Blood Urea Nitrogen BUN mg/dL	23 - 26	27 – 31	> 31	Requires dialysis
Creatinine – mg/dL	1.5 – 1.7	1.8 - 2.0	2.1 – 2.5	> 2.5 or requires dialysis
Calcium – hypocalcemia mg/dL	8.0 - 8.4	7.5 – 7.9	7.0 - 7.4	< 7.0
Calcium – hypercalcemia mg/dL	10.5 - 11.0	11.1 - 11.5	11.6 - 12.0	> 12.0
Magnesium – hypomagnesemia mg/dL	1.3 – 1.5	1.1 – 1.2	0.9 – 1.0	< 0.9
Phosphorous – hypophosphatemia mg/dL	2.3 – 2.5	2.0-2.2	1.6 – 1.9	< 1.6
CPK – mg/dL	1.25 – 1.5 x ULN***	1.6 – 3.0 x ULN	3.1 –10 x ULN	> 10 x ULN
Albumin – Hypoalbuminemia g/dL	2.8 - 3.1	2.5 – 2.7	< 2.5	
Total Protein – Hypoproteinemia g/dL	5.5-6.0	5.0 - 5.4	< 5.0	
Alkaline phosphate – increase by factor	1.1 – 2.0 x ULN	2.1 – 3.0 x ULN	. 3.1 – 10 x ULN	$> 10 \mathrm{x} \mathrm{ULN}$
Liver Function Tests –ALT, AST increase by factor	1.1 – 2.5 x ULN	2.6 – 5.0 x ULN	5.1 – 10 x ULN	> 10 x ULN
Bilirubin – when accompanied by any increase in Liver Function Test increase by factor	1.1 – 1.25 x ULN	1.26 – 1.5 x ULN	1.51 – 1.75 x ULN	> 1.75 x ULN
Bilirubin – when Liver Function Test is normal; increase by factor	1.1 – 1.5 x ULN	1.6 – 2.0 x ULN	2.0 – 3.0 x ULN	> 3.0 x ULN
Cholesterol	201 - 210	211 - 225	> 226	
Pancreatic enzymes _ amylase linase	$11 - 15 \times 11$ N	$16 - 20 \times III N$	$21 - 50 \times III N$	$> 5.0 \times III N$

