14.2. LABORATORY EVALUATIONS

Results from the local laboratory will be included in the reporting of this study for Hematology, Blood Chemistry and Urinalysis. A list of laboratory assessments to be included in the outputs, and a severity grading system is included in APPENDIX 3.

Presentations will use SI Units.

Quantitative laboratory measurements reported as "< X", i.e. below the lower limit of quantification (BLQ), or "> X", i.e. above the upper limit of quantification (ULQ), will be converted to X for the purpose of quantitative summaries, but will be presented as recorded, i.e. as "< X" or "> X" in the listings.

The following summaries will be provided for laboratory data:

- Observed values and change from baseline by visit (for quantitative measurements)
- Summary of qualitative clinical laboratory evaluations by visit
- Incidence of abnormal values at any time post-baseline according to normal range criteria
- Shift from baseline according to normal range criteria (for quantitative measurements and categorical measurements), by visit
- Shift from baseline to worst post-baseline value, according to severity grading system
- Summary of markedly abnormal post-baseline values
- Listing of patients with Grade 3 or above severity grades
- Box plots of absolute values over time and changes from baseline over time

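### SAP Appendix 3 puts the two bilirubin grading rows under the opposite liver-test labels to protocol Section 11.2, so bilirubin from about 1.25 to 3.0 × ULN is misgraded

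*SAP*

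**What the plan says.** Protocol Section 11.2, part B, gives two bilirubin rows. The tight limits apply under "Bilirubin – when accompanied by any increase in Liver Function Test increase by factor". The wide limits apply under "Bilirubin – when Liver Function Test is normal; increase by factor". The liver function tests are named in the row above them ("ALT, AST increase by factor").

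SAP Section 14.2.2 lists this scale first among its grading sources, and Appendix 3 codes both bilirubin rows to it (code a). There the tight limits stand beside "Liver Function test normal" and the wide limits beside "Liver Function test increase". Both labels carry an asterisk. The footnote begins "This is not specified in FDA guidance. Therefore, we take as reference to the" and goes on to mention Hy's Law criteria, with AST and ALT as the parameters to consider. Part of it is cut off in the text available for review.

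SAP Section 14.2 uses the laboratory grades in three outputs: "Shift from baseline to worst post-baseline value, according to severity grading system", the summary of markedly abnormal post-baseline values, and the listing of patients at Grade 3 or above.

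**The concern.** Both documents claim the same scale and use the same two sets of numbers, but each set is attached to the opposite condition. On the protocol scale, a given bilirubin is graded more severely when a liver test is also raised. As printed, the SAP grades it more severely when liver tests are normal.

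Safety is the primary objective. The Grade 3-or-above listing is where a reader would look for patients with a notable bilirubin rise, and over part of the range it would show the wrong ones. Protocol Section 7.1 also has adverse events recorded on the Section 11.2 scale, so one bilirubin abnormality could carry one grade in the AE tables and another in the laboratory tables.

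**Working it through.** **Inputs** (multiples of ULN; protocol Section 11.2 part B and SAP Appendix 3)

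| Source | Liver tests | Grade 1 | Grade 2 | Grade 3 | Grade 4 |
|---|---|---|---|---|---|
| Protocol | raised | 1.1–1.25 | 1.26–1.5 | 1.51–1.75 | >1.75 |
| SAP | raised | 1.1 to <1.5 | 1.5 to <2.0 | 2.0 to <3.0 | ≥3.0 |
| Protocol | normal | 1.1–1.5 | 1.6–2.0 | 2.0–3.0 | >3.0 |
| SAP | normal | 1.1 to <1.25 | 1.25 to <1.5 | 1.5 to <1.75 | ≥1.75 |

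**Step 1: labels as printed.** Grade the same value by both documents, assuming *raised* means the same in each. The protocol's normal-test row has a gap between 1.5 and 1.6 and an overlap at 2.0; values there are left out.

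| Bilirubin (× ULN) | Liver tests | Protocol grade | SAP grade |
|---|---|---|---|
| 1.26 to <1.5 | raised | 2 | 1 |
| 1.51 to 1.75 | raised | 3 | 2 |
| >1.75 to <2.0 | raised | 4 | 2 |
| 2.0 to <3.0 | raised | 4 | 3 |
| 1.25 to <1.5 | normal | 1 | 2 |
| 1.5 | normal | 1 | 3 |
| 1.6 to <1.75 | normal | 2 | 3 |
| 1.75 to <2.0 | normal | 2 | 4 |
| >2.0 to 3.0 | normal | 3 | 4 |

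Below 1.25 and above 3.0 × ULN the grades agree.

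**Step 2: the Grade 3 line.** With raised tests, 1.51 to <2.0 × ULN is protocol Grade 3 or 4 but SAP Grade 2, so these patients drop out of the listing. With normal tests, 1.6 to <2.0 × ULN is protocol Grade 2 but SAP Grade 3 or 4, so these patients enter it.

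**Step 3: exchange the two SAP labels.** Comparing the grades over 0.9 to 5.0 × ULN in steps of 0.001, with the protocol bands read as continuous and their upper limits inclusive, the SAP then matches the protocol everywhere except at exact cut points. The residual arises because the SAP puts a value equal to a limit in the higher grade and the protocol puts it in the lower. This is the pattern of a transposed label.

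**Step 4: if the definitions of *raised* differ.** Suppose the SAP's limit is stricter than the protocol's, which counts any increase. A patient raised by the protocol but normal by the SAP is then graded correctly as printed, except at exactly 1.25, 1.5 and 1.75. After a label exchange alone, that patient would be misgraded from 1.26 to <3.0 × ULN and lost from the listing from 1.51 to <2.0. Patients who are normal under both definitions, or raised under both, are misgraded as in Step 1 either way.

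**Minor, same appendix: BUN.** The protocol limits are 23, 26 and 31 mg/dL; the SAP cut points are 8.211, 9.75 and 11.625 mmol/L. 8.211/23 = 0.357, but 9.75/26 = 0.375 and 11.625/31 = 0.375. No single conversion factor gives all three, and neither document states one. Assuming 0.357, the SAP cut points equal 23.0, 27.31 and 32.56 mg/dL, so among whole values from 20 to 35 mg/dL, 27 and 32 are graded one too low. Assuming 0.375, 22, 26 and 31 are graded one too high. Factors tried from 0.365 to 0.373 misgrade no whole value, so the effect is small.

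**The case against.** The strongest counter-argument is the footnote. It is the only explanation of the two labels, it says a point is not specified in the guidance, and part of it is missing here. The missing part may define *raised*, and Step 4 shows that a stricter definition would leave some patients correctly graded as printed. That part stands, and the size of the effect must be stated conditionally. It does not rescue the table, because patients who are normal under both definitions, or raised under both, are misgraded whatever the missing words say. The limits themselves are specified in the scale, and the legible words concern which liver tests count.

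The consequence is also limited. Only bilirubin between about 1.25 and 3.0 × ULN is affected, only about 1.5 to 2.0 crosses the Grade 3 line, and among about 30 patients the number affected could be zero. Against that, protocol Section 4.1 sets no bilirubin, AST or ALT limit for entry and admits visceral metastasis, so nothing in eligibility excludes such values.

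Finally, the protocol calls its laboratory values guidelines dependent on institutional norms. The bilirubin limits are already multiples of the local ULN, so this does not explain exchanged labels. A table broken in PDF extraction is unlikely, since each SAP label sits on the same line as its limits.

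**Conclusion.** The bilirubin grading in SAP Appendix 3 is wrong as written. The contradiction with protocol Section 11.2 is certain. The full grade changes in Step 1 rest on *raised* meaning the same in both documents.

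The reach is confined to bilirubin in the three grade-based outputs. The primary laboratory endpoint in protocol Section 2.2.1 (changes, and shifts to abnormal values) does not use these grades. Observed values, normal-range categories (SAP Section 14.2.1) and AE severity (SAP Section 14.1.1.1) are unaffected. No formal test is planned (SAP Section 6.6), and no decision rule depends on the grades. It should be fixed before the graded outputs are relied on, but it does not threaten the main safety analysis. The BUN discrepancy adds no weight to this.

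**What to change.** 1. State in the Appendix 3 footnote the AST/ALT limit that counts as raised, and confirm that it matches the protocol's wording, under which any increase counts. Settle this first, because exchanging the labels alone may not restore the protocol grades.
2. Exchange the two bilirubin row labels so that the tight limits go with raised tests and the wide limits with normal tests. If the departure is intended, say so and give the reason.
3. Minor: use one stated BUN conversion factor, with each upper limit kept in the lower grade as in the protocol. Assuming 0.357, the limits are 23 × 0.357 = 8.211, 26 × 0.357 = 9.282 and 31 × 0.357 = 11.067 mmol/L. Assuming 0.375, they are 8.625, 9.75 and 11.625 mmol/L.

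The cost is an appendix correction and a re-run of the laboratory grading program. No new data are needed.

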6.5.3. Clinical Laboratory Assessments

Clinical laboratory assessments for safety monitoring will be performed by an accredited local laboratory. Blood and urine samples for hematology, serum chemistry and urinalysis, will be prepared using standard procedures.

PSA sample will be collected at Screening (unless performed within one month of enrollment and results are available), and results will be entered into the eCRF.

The following laboratory tests will be performed at Screening, Day 1 (after the administration of the IP), Day 7, and Day 28:

- Hematology: White blood cell (WBC) count with differential, red blood cell (RBC) count, Hb, hematocrit, platelet count, mean corpuscular volume (MCV).
- Blood chemistry profile: albumin, alkaline phosphatase (AP), alanine transaminase (ALAT), aspartate transaminase (ASAT), blood urea nitrogen (BUN), corrected calcium, chloride, creatinine, eGFR (preferably CKD-EPI), glucose, uric acid, gamma-glutamyl transpeptidase (GGT), lactate dehydrogenase (LDH), potassium, sodium, total bilirubin and total protein.
- Urinalysis: (dipstick), appearance, color, pH, specific gravity, protein, glucose and occult blood, RBC and WBC counts, Casts per low power field (Casts/lpf), Protein (dipstick test accepted).

Table 2 summarizes general laboratory assessments to be performed.

Hematology	Blood Chemistry	Urinalysis [*]
• WBC with differential	• BUN	• Appearance
• RBC	• Serum creatinine	• Color
• Platelets	• eGFR	• pH
• Hb	• Albumin	• Specific gravity
• MCV	• Total bilirubin	• Glucose
• Hematocrit	• AP	• Occult blood
• PSA (Screening visit only)	• AST/ASAT	• RBC/hpf
	• ALT/ALAT	• WBC/hpf
	• Gamma-GT	• Casts/lpf
	• Sodium	• Protein (dipstick test accepted)
	• Potassium	
	• Chloride	
	• LDH	
	Corrected Calcium	
	• Glucose	
	• Total protein	
	• Uric acid	

 Table 2
 Summary of Laboratory Assessments

*A urine sample will be collected at each visit and analyzed at the clinical site if dipstick results are abnormal. WBC = white blood cell; RBC = red blood cell; Hb = hemoglobin; MCV = mean corpuscular volume; PSA = prostate specific antigen; BUN = blood urea nitrogen; eGFR = estimated glomerular filtration rate; AST/ASAT = aspartate aminotransferase; ALT/ALAT = alanine aminotransferase; gamma-GT = gamma glutamyl transferase; LDH = lactate dehydrogenase; pH = potential of hydrogen; hpf = high power field; lpf = low power field.

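### SAP Appendix 3 grades every glucose value on the fasting row of the protocol's toxicity scale, although no sample is required to be fasting, so non-fasting values of 100 to 200 mg/dL are graded one step too high (two at exactly 125)

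*SAP*

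**What the plan says.** **The protocol scale.** The laboratory tables in protocol Section 11.2 label the entry "Glucose – Hyperglycemia Fasting – mg/dL Random – mg/dL", which is two rows in one cell. Grade 1 reads "100 – 110 110 – 125" (fasting, then random) and Grade 2 reads "111 – 125 126 – 200". Grade 3 is above 125 fasting and above 200 random. Grade 4 is defined by an event, not a value.

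**The SAP.** Appendix 3 assigns glucose to code a, which is this scale, and gives one hyperglycemia row with no fasting or random qualifier:

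- Grade 1: "\geq 5.55 - < 6.105 \text{ mmol/L"
- Grade 2: "\geq 6.105 - < 6.9375 \text{ mmol/L"
- Grade 3: "\geq 6.9375 \text{ mmol/L"

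**Sampling.** Protocol Section 6.5.3 says: "The following laboratory tests will be performed at Screening, Day 1 (after the administration of the IP), Day 7, and Day 28". No fasting condition appears there, in the schedule of procedures (Table 1), or in the visit descriptions of Sections 6.2 to 6.4. The only meal-related instruction is for the ECG (Section 6.5.5.1).

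**Use of the grades.** SAP Section 14.2 plans a shift table to the worst post-baseline grade, a summary of markedly abnormal values, and this output: "Listing of patients with Grade 3 or above severity grades".

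**The concern.** The SAP claims the protocol's scale but keeps only the half meant for fasting samples. The protocol gives no reason to treat the samples as fasting. The Day 1 sample is drawn after injection at no stated time, from patients who arrive in the morning (Section 6.3) and should stay on site for a further 6 hours (Section 5.4). On a non-fasting sample, the fasting row produces a higher grade than the scale the SAP names.

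This matters because safety is the primary objective, laboratory change is among the primary endpoints, and the design is single-arm. No comparator group would show that the same row inflates hyperglycemia grades everywhere. With groups of about 12, one patient listed at Grade 3 instead of Grade 2 is 1/12 = 8.3% of a group.

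**Working it through.** **Step 1. Reproduce the SAP limits.** The conversion factor is implied by the SAP's own hypoglycemia limits: 2.4975/45 = 3.0525/55 = 3.6075/65 = 3.8295/69 = 0.0555 mmol/L per mg/dL. Applied to the protocol's hyperglycemia limits:

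- 100 × 0.0555 = 5.55
- 110 × 0.0555 = 6.105
- 125 × 0.0555 = 6.9375
- 200 × 0.0555 = 11.1

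The first three are the SAP's limits exactly. They are the Grade 1 lower limit and the Grade 1 and Grade 2 upper limits of the fasting row. The random Grade 3 limit, 11.1 mmol/L, does not appear in Appendix 3.

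**Step 2. Grade whole mg/dL values three ways.** The SAP bands use ≥ 5.55, ≥ 6.105 and ≥ 6.9375 mmol/L. The protocol rows are used as printed.

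| Glucose (mg/dL) | SAP | Protocol fasting | Protocol random | SAP minus random |
|---|---|---|---|---|
| 95-99 | 0 | 0 | 0 | 0 |
| 100-109 | 1 | 1 | 0 | +1 |
| 110 | 2 | 1 | 1 | +1 |
| 111-124 | 2 | 2 | 1 | +1 |
| 125 | 3 | 2 | 1 | +2 |
| 126-200 | 3 | 3 | 2 | +1 |
| over 200 | 3 | 3 | 3 | 0 |

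All 76 whole values from 125 to 200 are Grade 3 under the SAP. On the random row, 75 of them are Grade 2 and one (125) is Grade 1.

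**Step 3. Separate the two causes.** At exactly 110 and 125 mg/dL the SAP is one grade above even the fasting row, because it starts the next band with ≥ at the upper limit of the previous one. Other Appendix 3 parameters, such as ALT and alkaline phosphatase, use the same convention. At 125, one of the two extra grades comes from that convention and one from the missing random row. Everywhere else from 111 to 200 the extra grade comes from the missing row alone.

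**Step 4. Trace the outputs.** The Grade 3+ listing and the shift-to-worst-grade table use these bands directly. The markedly abnormal summary does so only if that column heading covers Grades 3 and 4. The extracted table is broken and places the heading differently from page to page. In one place it sits above Grade 3, which suggests that reading without proving it. Observed values, change from baseline, normal-range incidence and shifts, and box plots do not use the bands.

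**The case against.** **The stricter row may be deliberate.** Without fasting status, the fasting row errs toward over-reporting, in line with the SAP's worst-case rules for missing severity, relatedness and treatment emergence. But the SAP states those rules openly. Here it cites the protocol's scale and declares no stricter one.

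**The scale calls its values guidelines that depend on institutional parameters.** It does, but that concerns local reference ranges and does not merge two separately defined rows. The medical-advisor review in SAP Section 14.2.2 covers only flagged parameters, and the visible Grade 1-3 glucose bands are numeric and unflagged.

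**The consequences are limited.** This stands. There is no formal testing, the ungraded laboratory summaries are untouched, and nothing converts a SAP laboratory grade into an adverse event. Three stronger inferences should be avoided:

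- A reader might infer that normal values are reported as severe. The documents do not support this: the random row already makes 126-200 mg/dL Grade 2 and 125 Grade 1. The fault is over-grading of values that are already graded, plus 100-109, which moves from 0 to 1.
- A reader might infer a spurious shift to Grade 3 after the product. That needs a fasting Screening sample and a fed Day 1 sample, and neither is documented. One row grades both visits, so stable glucose shows no shift. The Day 1 ECG, taken just after injection, should not closely follow a meal; this does not bind the blood draw, but it weakens the assumption of a recent one.
- A reader might infer that the primary endpoint itself is wrong. The changes from baseline and normal-range shifts that make up the laboratory part of it do not depend on these bands.

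**Conclusion.** The point holds. Appendix 3 is inconsistent with the scale it cites, and for non-fasting samples the error always runs upward: one grade at 100-124 and 126-200 mg/dL, and two at exactly 125, where one grade belongs to the ≥ convention. The Grade 3 threshold for such samples falls from above 200 mg/dL (11.1 mmol/L) to 125 mg/dL (6.9375 mmol/L). Random values of 125-200 mg/dL enter the Grade 3+ listing and are treated as Grade 3 in the shift-to-worst table when the protocol scale makes them Grade 1 or 2. The markedly abnormal summary is affected only if its heading covers Grade 3.

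This rests on at least some samples being non-fasting. The protocol permits that but does not state it. The eCRF and table templates are not in the documents, so fasting status may be collected, but the SAP has no rule that would use it. How many patients are affected cannot be estimated. The change should be made before the grade-based tables are produced.

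**What to change.** Reconcile Appendix 3 with protocol Section 11.2 by adding the random row in SI units: Grade 1 from 6.105 to 6.9375 mmol/L, Grade 2 above 6.9375 to 11.1, and Grade 3 above 11.1. The event-based Grade 4 is unchanged. Since no fasting is required, apply this one row to all scheduled glucose values, baseline and post-baseline alike, and footnote the choice. Samples documented as fasting may also be shown on the fasting row, in the listing only.

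Choosing the row sample by sample would be worse. A fasting Screening value of 130 mg/dL would be Grade 3 and a random Day 1 value of 180 mg/dL Grade 2, so a rise of 50 mg/dL would appear as an improvement in the shift table.

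Convert with the same factor of 0.0555, or grade in mg/dL. With division by 18.016, 125 and 200 mg/dL become 6.9383 and 11.1012 mmol/L and would cross the limits.

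The cost is one table row, a footnote and a small programming change. Appendix 3 already carries two conditional rows for bilirubin, so the format exists. The downside is that a truly fasting sample is graded more leniently in the summary tables; its observed value, change from baseline and normal-range category still show it.
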